10.2 PRIMARY ANALYSIS

The primary endpoint of the study will be the overall participant satisfaction based on CSQ Item question #1 at 12 weeks after the final treatment (measured at week 12 for participants who received 1 treatment session, week 20 for 2 treatment sessions) for non-invasive fat reduction in CoolSculpting participants, including participants who receive treatment in the abdomen alone, flanks alone, or both abdomen and flanks.

The CSQ consists of 3 versions: CSQ-Abdomen, CSQ-Flank, CSQ-Abdomen and Flank; Participants with abdomen only treatment will be administered only the CSQ-Abdomen. Participants with flank only treatment will be administered only the CSQ-Flank version. Participants with both abdomen and flank treatments will be administered all 3 versions (CSQ-Abdomen, CSQ-Flank, and CSQ-Abdomen and Flank)); however, only CSQ-Abdomen and Flank will be used for the primary analysis. In each version, the CSQ Item question #1 is “Rate your overall satisfaction with the fat reduction procedure on the treated area”, with the following categories:

- Very satisfied
- Satisfied
- Neither satisfied nor dissatisfied
- Dissatisfied
- Very dissatisfied

‘Very satisfied’ and ‘Satisfied’ will be categorized as a new category, ‘Satisfied’.

The number and percentage of participants will be presented by category at 12 weeks after the final treatment, regardless of the CSQ version.

Furthermore, the 95% confidence interval on the proportion by category at 12 weeks after the final treatment, regardless of the CSQ version will be calculated using normal approximation method.

10.3 **SECONDARY ANALYSES**

All secondary endpoints will be measured at Week 12 for participants who received 1 treatment session and at Week 20 for participants who received 2 treatment sessions. The following analyses will be provided:

- Proportion of participants by treated area(s) (abdomen, flanks, and both abdomen and flanks) with “satisfied” or “very satisfied” on the CSQ Item #1.
- Proportion of participants by number of treatment cycles who received 1 or 2 treatment sessions with “satisfied” or “very satisfied” on CSQ Item #1.
- Proportion of participants with “Satisfied” or “Very Satisfied” on CSQ Item #1 by BMI categories (18.5 - < 25, 25 - ≤ 30)
- Mean change in volume of fat from baseline as measured by 3D photography.

The count and percentage of participants with the same categories as the primary endpoint for CSQ Item #1 will be summarized and the 95% CIs for the percentages will be calculated.

Descriptive summary statistics of change in volume of fat from baseline will be provided by visit.

[REDACTED]

[REDACTED]

[REDACTED]

[REDACTED]

[REDACTED]

[REDACTED]

[REDACTED]

[REDACTED]

[REDACTED]

- █ [REDACTED]
- █ [REDACTED]
- █ [REDACTED]
- █ [REDACTED]
- █ [REDACTED]

[REDACTED]

[REDACTED]

[REDACTED]

[REDACTED]

[REDACTED]

11.1 **SAFETY ANALYSES**

The safety analyses will be based on the safety population.

11.2 **ADVERSE EVENTS**

Adverse events (AEs) will be collected throughout the study beginning with the first treatment visit. Adverse events will be coded by system organ class and preferred term using the *Medical Dictionary for Regulatory Activities*, version 22.0 or newer. AEs, AE severity, and causality are defined in the protocol (Section 11.1).

An AE will be considered a treatment-emergent (TEAE) if the AE began or worsened (increased in severity or became serious) on or after the treatment start date and time. An AE is considered an ADE if the AE with a reasonable possibility (Possible, Probable, or Causal relationship) that the device caused the event. An AE is considered a study procedure related AE if the AE with a reasonable possibility (Possible, Probable, or Causal relationship) that the procedure caused the event.

Overall summary of TEAEs, SAEs, ADEs, SADEs, study procedure related AEs, TEAEs leading to study discontinuation, and deaths will be presented as total and by treatment session. AEs/ADEs occurred on or after the date of treatment sessions 1 and before the date of treatment session 2 are counted for treatment session 1; AEs/ADEs occurred on or after the date of treatment sessions 2 are counted for treatment sessions 2.

The number and percentage of participants will be summarized by System Organ Class (SOC) and Preferred Term (PT), with or without by severity, as total and by treatment session as follows:

- TEAEs by SOC and PT
- TEAEs by SOC, PT, and severity
- ADEs by SOC and PT
- ADEs by SOC, PT, and severity
- Study Procedure Related AE by SOC and PT
- Treatment-emergent Serious AEs (SAEs) by SOC and PT
- Serious ADEs (SADEs) by SOC and PT
- TEAEs leading to study discontinuation by SOC and PT

The AE summary tables by SOC and PT will be presented with SOC in alphabetical order and in decreasing frequency within each SOC.

If more than 1 AE is coded to the same preferred term for the same participant, the participants will be counted only once for that preferred term using the greatest severity and strictest causality for the summarization by severity and causal relationship.

In addition, deaths, SAEs (including SADEs) and TEAEs leading to study discontinuation will be listed separately.

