## **Statistical Analysis**

The primary endpoint of the study will be the overall patient satisfaction based on the CSQ Item #1 at 12 weeks after the final treatment session (measured at Week 12 for subjects who receive 1 treatment session, Week 20 for 2 treatment sessions) for non-invasive fat reduction in CoolSculpting subjects who receive treatment in abdomen alone, flanks alone, or both abdomen and flanks. Subjects who have reported 'Very satisfied' and 'Satisfied' will be categorized as 'Satisfied.' The counts and percentage will be summarized and the 95% confidence interval (CI) on the percentage will be calculated with normal approximation.

Secondary efficacy endpoints related to overall patient satisfaction rate on CSQ Item #1 at 12 weeks after the final treatment session will also be summarized along with 95% CIs. Descriptive summary statistics for change in volume of fat from baseline and [REDACTED]

Safety endpoints will be presented as summary tables describing frequency and type of events.

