In a Chinese population study, investigators compared the clinical efficacy and patient satisfaction of a novel cryolipolysis device (ZELTIQ®) for body contouring after a single treatment and after 2 treatments in a commercial setting. Twenty-one subjects received a single treatment lasting 60 minutes, and 12 subjects received 2 treatments lasting 60 minutes each, on average of 3 months apart. The thickness of fat at the treatment site is measured using a calliper, as well as standardized clinical photos, that were collected at baseline and 2 months post-treatment. There was a significant improvement ( $p < 0.0001$ ) in the first group of subjects and after both treatments compared to the baseline in the second group of subjects for treatment on the abdomen. Fifty-seven percent of patients thought the treatment reached or exceeded their expectations, whereas 43% expected a more dramatic effect. Subjectively, 80% felt satisfied to very satisfied, and the rest were indifferent. Eighty-six percent would consider having non-invasive cryolipolysis performed on another part of their body and would consider recommending this treatment to family and friends ([Shek et al, 2012](#)).

Based on these studies, cryolipolysis is well tolerated, has a high patient satisfaction, and is effective in reducing fat in the abdominal region.

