## 10 STATISTICAL METHODS

The purpose of the study is to obtain PROs and have more subjects treated and studied at international sites. There is no statistical hypothesis to prove in this study. More details on the methods of statistical analysis, on statistical summary, and on the derivation of some statistical variables can be found from the statistical analysis plan.

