#### **10.3.2.1 Primary Analyses**

The primary endpoint will be CSQ Item #1 measured at Week 12 for subjects who receive 1 treatment session and at Week 20 for subjects who receive 2 treatment sessions.

Subjects who have reported 'Very satisfied' and 'Satisfied' will be categorized as 'Satisfied.' The counts and percentage will be summarized and the 95% CI on the percentage will be calculated with normal approximation.

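### SAP 10.2 applies normal-approximation 95% CIs to each CSQ Item #1 response category, and the visible text has no small-count rule; this is sound for pooled 'Satisfied' but not for sparse categories

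*SAP*

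**What the plan says.** SAP 10.2 lists five responses to CSQ Item #1, pools the top two as 'Satisfied', and presents counts and percentages by category. It then requires the "95% confidence interval on the proportion by category at 12 weeks after the final treatment", which "will be calculated using normal approximation method".

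SAP 10.3 covers treated area, number of treatment cycles and BMI group. Its instruction for these tables refers back to SAP 10.2: "the same categories as the primary endpoint for CSQ Item #1 will be summarized and the 95% CIs for the percentages will be calculated". No interval method is named.

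The protocol is narrower. In section 10.3.2.1, straight after pooling the top two responses, it says that "the 95% CI on the percentage will be calculated with normal approximation". The synopsis (Statistical Analysis) says the same of the pooled percentage. Of the secondary satisfaction endpoints it says only that they "will also be summarized along with 95% CIs".

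The visible SAP text, including the data handling conventions in 17.1, has no rule for zero or small counts, no score or exact alternative, and no truncation of limits at 0 or 100%.

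**The concern.** The normal-approximation (Wald) interval takes its width from the observed proportion. When a category has few responses, the estimated variance shrinks towards zero and the symmetric interval fits a skewed distribution badly. An empty category gets an interval of no width, which reads as certainty. A category with a handful of responses gets a lower limit below zero. Over repeated studies, such intervals contain the true rate less often than 95%.

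The protocol uses the method only where the proportion is mid-range. SAP 10.2, read literally, carries it to every response level, including 'Dissatisfied' and 'Very dissatisfied', and SAP 10.3 asks for intervals on those levels in smaller groups. What is at stake is misleading precision for rare answers, which are the answers a reader would look to for evidence of dissatisfaction.

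**Working it through.** **Inputs.** From SAP 15.0 and protocol 10.1: satisfaction of 65.8% in 19 and 63.3% in 60 subjects, an expected rate of 63.9%, 98 evaluable participants, a 10-point margin and 10% dropout. Protocol 7.3.1 plans about 100 enrolled, so 100 × 0.9 = 90 evaluable is also checked. True rates per category are not given; 1% to 12% is assumed. Secondary group sizes are not given; 98/3 ≈ 33, for three equal treated-area groups, is assumed.

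**The plan's own figures.** (19 × 65.8 + 60 × 63.3)/79 = 63.9%, as stated. The plain margin at n = 98 is 1.96 × √(0.639 × 0.361/98) = 9.5 points. With a continuity correction it is 9.5 + 100/(2 × 98) = 10.0 points, which matches the stated 10%. The SAP does not say whether its intervals are continuity-corrected, so both forms are checked.

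**Pooled 'Satisfied'.** Exact coverage is the sum of binomial probabilities over all counts whose interval contains the true rate. At 63.9% and n = 98, plain Wald covers 95.3%. The method is sound here.

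**Intervals at small counts, n = 98.** Wald: p ± 1.96√(p(1−p)/n). Wilson: [p + z²/2n ± z√(p(1−p)/n + z²/4n²)]/(1 + z²/n), with z = 1.96.

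| Count | Wald | Wilson | Exact |
|---|---|---|---|
| 0 | 0% to 0% | 0% to 3.8% | 0% to 3.7% |
| 1 | −1.0% to 3.0% | 0.2% to 5.6% | 0.03% to 5.6% |
| 2 | −0.8% to 4.8% | 0.6% to 7.1% | 0.3% to 7.2% |
| 3 | −0.3% to 6.5% | 1.1% to 8.6% | 0.6% to 8.7% |
| 4 | 0.2% to 8.0% | 1.6% to 10.0% | 1.1% to 10.1% |

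**Average coverage over assumed rates.** Wald coverage oscillates with the true rate (n = 98: 62.6% at 1%, 85.8% at 2%, 94.7% at 3%, 87.0% at 5%, 88.9% at 8%, 94.6% at 12%), so averages over ranges are more informative than single points.

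| n | True rates | Plain Wald | Continuity-corrected | Wilson | Exact |
|---|---|---|---|---|---|
| 98 | 1–2% | 76% | 76% | 96% | 99% |
| 98 | 1–5% | 86% | 88% | 96% | 98% |
| 98 | 5–12% | 92% | 95% | 95% | 97% |
| 90 | 1–2% | 73% | 73% | 96% | 99% |
| 90 | 1–5% | 85% | 87% | 96% | 98% |
| 90 | 5–12% | 92% | 94% | 95% | 97% |

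A continuity correction largely repairs the 5–12% range but not 1–2%.

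**Chance of a defective interval.** At n = 98 a count of 0 to 3 gives zero width or a negative limit. Its probability is 98% at a true rate of 1%, 87% at 2%, 27% at 5%, 4% at 8% and 0.2% at 12%.

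**Secondary groups, n = 33.** The same counts are defective. For 3/33 the lower limit is 0.091 − 1.96√(0.091 × 0.909/33) = −0.7%; for 4/33 it is 0.121 − 1.96√(0.121 × 0.879/33) = +1.0%. The chance of a count of 0 to 3 is 92% at a 5% rate, 73% at 8% and 43% at 12%. If the normal approximation is carried into SAP 10.3, sparsity there does not need rare rates.

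**The case against.** **The interval may be meant only for the pooled endpoint.** The sentence in SAP 10.2 comes soon after the pooling rule, the protocol attaches the method to the pooled percentage, and SAP 18.0 declares no change from the protocol. That reading is possible but less literal. The sentence just before uses the same phrase for the tabulated counts, and SAP 10.3 repeats that intervals are wanted for the same categories. If the narrower reading is intended, saying so in SAP 10.2 would settle it there.

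**Sparsity is assumed.** This stands. The planned rate leaves 36.1% not satisfied; split equally over three categories that is 12% each, where plain Wald covers 94.6% at n = 98 (91.6% at n = 90). A reader might infer from the Chinese population study in protocol 5.1.1 that the dissatisfied categories will be near empty: "Subjectively, 80% felt satisfied to very satisfied, and the rest were indifferent". The documents do not support that. The study describes treating 33 subjects ("Twenty-one subjects received a single treatment lasting 60 minutes, and 12 subjects received 2 treatments lasting 60 minutes each"), yet no whole count out of 33 gives its 57%, 43%, 80% or 86%, so the number of respondents is unclear. With 20 or 21 respondents, no dissatisfied answers is compatible with a true rate up to 1 − 0.05^(1/20) = 13.9% or 1 − 0.05^(1/21) = 13.3% (one-sided 95% bounds).

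**A rule may exist elsewhere.** Parts of the SAP are redacted or lost in extraction, and table specifications are in a separate document. The statement that there is no small-count rule therefore covers the visible text only. SAP 10.2 itself is not redacted.

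**The consequence is small.** This also stands. The protocol says "There is no statistical hypothesis to prove in this study", and counts and percentages are shown too, so an alert reader would recognise a 0% to 0% interval as an artefact. The counts lessen the harm; they do not make the interval valid.

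**Conclusion.** The point holds for categories that turn out sparse, on the literal reading of SAP 10.2 and the visible text. With n = 98, counts of 0 to 3 give a zero-width interval or a negative lower limit, and average coverage is 76% for true rates of 1–2% and 86% for 1–5%, against 96% with Wilson. In the whole evaluable population the problem lies mainly below a rate of about 5%; that threshold is a judgement, because Wald coverage is erratic. In secondary groups, at the assumed size of 33, it can arise at ordinary rates. The category rates and group sizes are assumptions throughout.

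A reader might infer that the primary result is compromised. It is not: pooled 'Satisfied' has 95.3% coverage, and the primary estimate, its interval and the sample size are unaffected. The benefit is confined to descriptive tables, so the change is worth making but optional.

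**What to change.** - **SAP 10.2:** keep the normal approximation for the pooled 'Satisfied' proportion, as the protocol specifies, and specify Wilson score 95% intervals for the individual response categories.
- **SAP 10.3:** specify Wilson for the individual categories. State one method for pooled 'Satisfied' and note any difference from the primary table, so that the same proportion does not change method between tables unexplained.
- **Cohort and subgroup tables (SAP 10.1 and 12.1):** apply the same rule wherever intervals are shown; the text does not say whether they will be.

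The cost is two short SAP edits and a standard software option. Intervals for rare categories become slightly wider: for 2/98 the width goes from 5.6 to 6.6 points. No protocol edit is needed, because the protocol fixes the method only for the pooled primary percentage. Data collection does not change.

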11.3 CLINICAL LABORATORY PARAMETERS

Listing for pregnancy test results will be provided.

[REDACTED]

- [REDACTED]
- [REDACTED]
- [REDACTED]
- [REDACTED]
- [REDACTED]
- [REDACTED]
- [REDACTED]

[REDACTED]

[REDACTED]

[REDACTED]

12.1 **SUBGROUP ANALYSIS**

The following subgroup analyses for the primary and secondary effectiveness endpoints will be provided:

1. Subgroup analysis for Chinese participants. Chinese participants are defined as participants with race of Asian – Chinese per study CRF.
2. Subgroup analysis for Asian participants. Asian participants are defined as participants with race of Asian – Chinese, Asian – Japanese, Asian – Korean, or Asian – Other, per study CRF.
3. Subgroup analysis for number of cycles (in 1 or 2 treatment sessions) used per body area per treatment session for satisfied (very satisfied, satisfied) vs neither satisfied/dissatisfied vs unsatisfied (dissatisfied, very dissatisfied).
4. Subgroup analysis for each site and each country.

For TEAEs and ADEs, the following summary tables will be provided as total and by treatment session for the subgroups (Chinese participants, Asian participants, number of treatment cycles, and country/site), respectively:

- TEAEs by SOC and PT
- TEAEs by SOC, PT, and severity
- ADEs by SOC and PT
- ADEs by SOC, PT, and severity

In addition, summaries on demographics, other baseline data (Sections 8.2, 8.3, and 8.4), exposure (Section 9.1), other effectiveness (Section 10.3), other safety data (Sections 11.2 and 11.3) will be provided for Chinese participants and Asian participants, respectively.

13.0 **HEALTH OUTCOMES ANALYSES**

Not applicable.

14.0 **INTERIM ANALYSIS**

No interim analysis is planned for this study.

15.0 **DETERMINATION OF SAMPLE SIZE**

The sample size will be based on providing reasonable precision for the estimate of the overall satisfaction rate.

Previous studies conducted on participants undergoing flank or abdominal fat reduction using CoolSculpting products reported moderately high overall satisfaction rate. The mean overall satisfaction rate was 65.8% from the study (protocol: ZA15-004) based on 19 participants, and 63.3% from another study (Protocol: ZA10-001) based on 60 participants. The weighted average of rates from the 2 studies, which is 63.9%, is now used as the initial estimate of the mean overall satisfaction rate for this planned study. A sample size of 98 participants would provide a 10% margin of error (associated with 95% confidence interval) for the estimate of the 63.9% expected rate. Allowing a 10% dropout during the study period, approximately 108 participants will be needed for recruitment into the study.

16.0 **STATISTICAL SOFTWARE**

Statistical analyses will be performed using version 

17.1 DATA HANDLING CONVENTIONS

Descriptive summaries include:

- Continuous variables will be summarized by number of participants and mean, SD, median, minimum, and maximum values.
- Categorical variables will be summarized by number and percentage of participants.

In general, data listing will be provided.

17.2 VISIT TIME WINDOWS

The analysis visit windows for effectiveness endpoints will be defined as follows

Error! Reference source not found. Effectiveness Analysis Visit Definitions

Analysis Phase	Analysis Visit (Derived)	Scheduled Study Visit (eCRF)	Window
Pretreatment	Baseline	Visit 2	Last assessment for which the assessment date is less than the treatment start date
Treatment	Final treatment	The final evaluations will be done on or +14 days of week 12 for participants who receive 1 treatment session; on or +14 days of week 20 for participants who receive 2 treatment sessions	Latest non-missing assessment after treatment start date

If the assessment date (or visit date, if the assessment date is unavailable) is on or after the date of the first study treatment, the study day is calculated as: assessment date – date of the first study treatment + 1. If the assessment date (or visit date, if the assessment date is unavailable) is before the date of the first study treatment, the study day is calculated as: assessment date – date of the first study treatment. Therefore, a negative day indicates a day before the start of the study intervention.

If multiple assessments were taken within an analysis window, the assessment obtained on the day closest to the target day will be used; in the case of a tie, the assessment obtained on the later day will be used in the analysis.

17.317.4**MISSING DATE OF THE LAST STUDY TREATMENT**

When the date of the last study treatment is missing for a participant in the Safety Population, all efforts should be made to obtain the date from the Investigator. If after all efforts are made it is still missing, the last available treatment record date will be used as the last treatment date.

17.5**MISSING SEVERITY ASSESSMENT FOR ADVERSE EVENTS**

If severity is missing for an AE that started before the date of the first study treatment, an intensity of mild will be assigned. If severity is missing for an AE that started on or after the date of the first study treatment, an intensity of severe will be assigned. The imputed values for severity assessment will be used for the incidence summary; the values will be shown as missing in the data listings.

17.6**MISSING CAUSAL RELATIONSHIP TO STUDY TREATMENT FOR ADVERSE EVENTS**

If the causal relationship to the study treatment is missing for an AE that started on or after the date of the first study treatment, a causality of yes will be assigned. The imputed values for causal relationship to study treatment will be used for the incidence summary; the values will be shown as missing in the data listings.

17.7**MISSING DATE INFORMATION FOR ADVERSE EVENTS**

The following imputation rules only apply to cases in which the start date for AEs is incomplete (i.e., partly missing).

Missing month and day

- If the year of the incomplete start date is the same as the year of the first study treatment, the month and day of the first study treatment will be assigned to the missing fields

- If the year of the incomplete start date is before the year of the first study treatment, *December 31* will be assigned to the missing fields
- If the year of the incomplete start date is after the year of the first study treatment, *January 1* will be assigned to the missing fields

Missing month only

- If only the month is missing, the day will be treated as missing and both the month and the day will be replaced according to the above procedure

Missing day only

- If the month and year of the incomplete start date are the same as the month and year of the first study treatment, the day of the first study treatment will be assigned to the missing day
- If either the year of the incomplete start date is before the year of the first study treatment or if both years are the same, but the month of the incomplete start date is before the month of the first study treatment, the last day of the month will be assigned to the missing day
- If either the year of the incomplete start date is after the year of the date of the first study treatment or if both years are the same, but the month of the incomplete start date is after the month of the date of the first study treatment, the first day of the month will be assigned to the missing day

If the stop date is complete and the imputed start date as above is after the stop date, the start date will be imputed by the stop date.

If the start date is completely missing and the stop date is complete, the following algorithm will be used to impute the start date:

- If the stop date is after the date of the first study treatment, the date of the first study treatment will be assigned to the missing start date
- If the stop date is before the date of the first study treatment, the stop date will be assigned to the missing start date

17.8**MISSING DATE INFORMATION FOR PRIOR OR
CONCOMITANT MEDICATIONS**

For prior or concomitant medications, including rescue medications, incomplete (i.e., partly missing) start dates and/or stop dates will be imputed. When the start date and the stop date are both incomplete for a participant, the start date will be imputed first.

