### 6.2 Endpoints

#### Primary Endpoint

The primary endpoint will be CSQ Item #1 measured at Week 12 for subjects who receive 1 treatment session and at Week 20 for subjects who receive 2 treatment sessions.

The analysis on the primary endpoint will be the proportion of subjects with “satisfied” or “very satisfied” on CSQ Item #1.

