##### 9.1.1.1 Cryolipolysis Satisfaction Questionnaire (CSQ) Subject Satisfaction Patient-Reported Outcome Survey

The CSQ is a 4-item PRO instrument that measures patient satisfaction with CoolSculpting treatment of the flank and abdomen. The questionnaire assesses patient satisfaction with treatment, visible fat reduction, improvement in fit of clothing, and overall effect of treatment. The CSQ consists of 3 versions: CSQ-Abdomen ([Appendix 17.4](#)), CSQ-Flank ([Appendix 17.5](#)), and CSQ-Abdomen and Flank ([Appendix 17.3](#)). Initial draft of the questionnaire was developed based on questions used in previous CoolSculpting studies and was revised based on hybrid concept elicitation and cognitive debriefing interviews with 6 patients.

The CSQ will be administered during office visits before treatment at Week 8 (Visit 4a) and during follow-up/exit visits at Weeks 12 (Visit 6, for patients who receive 1 treatment session) and 20 (Visit 7, for patients who receive 2 treatment sessions). Patients with abdomen only treatment will only be administered the CSQ-Abdomen version. Patients with flank only treatment will only be administered the CSQ-Flank version. Patients with both abdomen and flank treatment will be administered all 3 CSQ versions: CSQ-Abdomen, CSQ-Flank, and CSQ-Abdomen and Flank.

[REDACTED]

[REDACTED]

[REDACTED]

[REDACTED]

[REDACTED]

[REDACTED]

[REDACTED]

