4.0 INTRODUCTION

This statistical analysis plan (SAP) provides a more technical and detailed elaboration of the statistical analyses of the effectiveness and safety data as outlined and/or specified in the most recent protocol amendment of Study CMO-MA-PLS-0602 (version dated 20 Nov 2019). Specifications of tables, figures, and data listings are contained in a separate document.

Study CMO-MA-PLS-0602 is a multi-country, multi-center, non-randomized, open-label, single-arm, medical device post-marketing study in healthy volunteers with age ≥ 22 and ≤ 65 . All participants will undergo CoolSculpting® treatments(s) in an outpatient clinical setting. A treatment is comprised of timed segments of tissue cooling followed by massage.

[figure not shown]
The length of this study will be up to 20 weeks, not including the ≤ 7 days screening visit. Signed informed consent from the participants will be obtained before any study-related procedures are performed. All participants will be assigned a participant number sequentially based on the order in which the study participant is enrolled into the study. Participants meeting the inclusion criteria will be assigned to receive up to 2 treatment sessions 8 weeks apart and final follow-up 12 weeks after the final treatment (measured at week 12 for participants who receive 1 treatment session, or week 20 for 2 treatment sessions). Participants withdrawing from the study will be encouraged to complete the same final evaluations as participants completing the study according to this protocol, particularly safety evaluations.

No interim analyses are planned for this study.

Allergan Confidential
CoolSculpting[®]

Statistical Analysis Plan CMO-MA-PLS-0602

5.1 **OBJECTIVES**

Primary Objective

The primary objective is to evaluate overall patient satisfaction for non-invasive fat reduction in CoolSculpting® participants.

Secondary Objectives

1. To evaluate overall satisfaction for non-invasive fat reduction in abdomen alone, flank alone, and abdomen and flanks in CoolSculpting® participants.
2. To evaluate overall satisfaction for non-invasive fat reduction in CoolSculpting® participants by number of treatment cycles.
3. To evaluate overall satisfaction for non-invasive fat reduction in CoolSculpting® participants by BMI (normal: 18.5 to <25, overweight: 25 to ≤30).
4. To evaluate change in volume of fat after CoolSculpting® treatment(s) using 3D photography.

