10.1 EFFECTIVENESS ANALYSES

The effectiveness analyses will be based on the evaluable population. Baseline is defined as the last non-missing assessment before the first cycle of treatment.

In addition to the entire evaluable population, summaries will be provided for the following cohorts:

- Participants with 1 treatment session
- Participants with 2 treatment sessions

Some effectiveness parameters are also measured or reported at 8 weeks post treatment session #1. Descriptive summaries will be provided for this visit similar as for the effectiveness endpoints at the final visit.

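### SAP 10.1 and SAP 17.2 give conflicting baseline rules: an assessment made before treatment on the day of session 1 is baseline under one and rejected by the other

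*SAP*

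**What the plan says.** The SAP defines the effectiveness baseline twice.

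- SAP 10.1 (Effectiveness Analyses): "Baseline is defined as the last non-missing assessment before the first cycle of treatment". The cut-off is an event, the first cycle.
- SAP 17.2 (Visit Time Windows), baseline row, scheduled visit given as Visit 2: "Last assessment for which the assessment date is less than the treatment start date". The cut-off is a calendar date, and the inequality is strict.

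The only other row of the 17.2 table is the final evaluation, whose window is "Latest non-missing assessment after treatment start date".

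The endpoint that visibly needs a baseline is listed among the secondary analyses in SAP 10.3: "Mean change in volume of fat from baseline as measured by 3D photography". SAP 18.0 reports no change from the protocol, and the protocol text available contains no baseline definition that would settle the matter.

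**The concern.** A statistical programmer working from 10.1 and another working from 17.2 could both follow the SAP faithfully and select different baselines for the same participant. This happens whenever the pre-treatment assessment and session 1 share a date, a common arrangement in an outpatient device study.

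At stake is the change in fat volume. If 17.2 is applied as written, the same-day image is passed over. The baseline then becomes an earlier image, if one was taken, or is absent, and the change cannot be derived. The visible SAP text gives no rule for a missing baseline volume. Protocol 9.1.2 adds a further reason to have a single rule: the technician defines the region of interest on the baseline surface, so the image used there and the image the SAP calls baseline should be the same one.

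**Working it through.** The plan states no figure to reproduce here. The check is to apply both rules to the same assessments and then ask what the documents say about the date of Visit 2.

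**Step 1. Study day.** SAP 17.2 states that for an assessment "on or after the date of the first study treatment, the study day is calculated as: assessment date – date of the first study treatment + 1". For earlier dates nothing is added. So a date 7 days before session 1 is Day -7, a date 1 day before is Day -1, and the day of session 1 is 0 + 1 = Day 1.

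**Step 2. Apply the rules to an assessment taken before the first cycle.**

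| Assessment date | Study day | 10.1: before first cycle | 17.2 baseline: date < treatment date | 17.2 final: date > treatment date |
|---|---|---|---|---|
| 7 days before session 1 | -7 | accepted | accepted | outside |
| 1 day before session 1 | -1 | accepted | accepted | outside |
| Day of session 1 | 1 | accepted | rejected | outside |

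The rules differ only in the last line. There, 17.2 assigns the assessment to no analysis visit at all.

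**Step 3. Where does Visit 2 fall?** The evidence in the text is indirect.

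- SAP 4.0: "The length of this study will be up to 20 weeks, not including the ≤ 7 days screening visit". Two sessions 8 weeks apart plus 12 weeks of follow-up give 8 + 12 = 20 weeks, so the clock starts at session 1. No separate baseline visit is mentioned. An earlier-day Visit 2 could still sit inside the screening interval of up to 7 days, outside the 20 weeks.
- Protocol 9.2.3 lists Screening, Treatment 1 and Treatment 2 as separate time points for pregnancy testing, but gives none of them a visit number.
- Protocol 9.1.1.1: "The CSQ will be administered during office visits before treatment at Week 8 (Visit 4a"). This shows that the design places assessments before treatment at a treatment visit, but it concerns the questionnaire at session 2, not imaging at session 1.

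Together these make a same-day Visit 2 plausible without establishing it. The possible range for Visit 2 is from 7 days before session 1 to the day itself.

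**Step 4. Share affected.** If every baseline image is taken on an earlier date, 0%. If every one is taken on the day of session 1, 100%. Nothing in the documents narrows this.

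**Step 5. What is not affected.** Protocol 6.2: "The analysis on the primary endpoint will be the proportion of subjects with “satisfied” or “very satisfied” on CSQ Item #1". That proportion uses no baseline value, and the sample size rests on the precision of that proportion.

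**The case against.** The strongest answer is that the SAP already contains the right rule. The effectiveness section, 10.1, keeps a same-day assessment made before the first cycle, and a programmer who sees Visit 2 named in the 17.2 row would probably take the Visit 2 value whatever its date. On that view the problem is two wordings to tidy, in a study with no hypothesis to test, for one descriptive secondary endpoint. Much of this stands: the impact is limited, and a sensible programmer might resolve the conflict correctly. But nothing in the SAP gives 10.1 precedence, and the table of analysis windows is a natural specification for a programmer to implement.

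A reader might go further and infer that the baseline is certain to be discarded and the fat-volume endpoint lost. The documents do not support that. The content of the schedule table is not available, so the date of Visit 2 and the timing of the baseline image are unknown. An earlier image may exist and would serve under 17.2. And 10.1, read alone, loses nothing. For the same reason, any share between 0% and 100% would be a guess.

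**Conclusion.** The conflict between SAP 10.1 and SAP 17.2 is real and can be read directly from the two sections. For any participant imaged before treatment and treated on the same day, 17.2 would either substitute an earlier image or leave the change in fat volume missing, where 10.1 would use the image intended.

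How many participants this touches depends on one assumption that cannot be checked here, the day of Visit 2 relative to session 1, and on whether an earlier image exists. The size is therefore unknown, from none to all. The consequence is confined to effectiveness summaries that use a baseline, visibly secondary endpoint 4. It is worth correcting before database lock because it is a contradiction in a derivation rule, not merely a missing detail.

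**What to change.** Replace the window in the baseline row of SAP 17.2 with the 10.1 definition, extended to cover ordering within a day:

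*Last non-missing assessment on or before the date of the first treatment and before the start of the first treatment cycle; a scheduled Visit 2 assessment dated the same day as the first treatment is treated as pre-treatment unless a recorded time shows otherwise.*

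This changes one table cell. It gives the same result as now for every baseline on an earlier day, so it is harmless whichever visit layout applies. Cycle start times are already needed for the exposure summary in SAP 9.2, and SAP 11.2 already uses the treatment start date and time to define treatment-emergent events.

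There is a small cost. The documents do not say that the time of the 3D image is recorded. If it is not, the order of same-day records rests on the default that a scheduled Visit 2 assessment preceded treatment.
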